## 8.3. Variables

### 8.3.1. Exposure definitions

There are two types of triple therapy: single inhaler triple therapy (SITT) (Trelegly 100, other than Trelegly 100) and MITT as described below. Exposures of this study are Trelegly 100 and MITT.

1. Single inhaler triple therapy (SITT):
  - a. Trelegly 100 (FF/UMEC/VI delivered in an Ellipta inhaler)
  - b. SITTs other than Trelegly 100 (for secondary objective-d) only
2. Multiple inhaler triple therapy (MITT):
  - a. LAMA combined with fixed dose ICS/LABA (two devices), or
  - b. LAMA/LABA with ICS (two devices), or
  - c. Fixed dose ICS, LABA, and LAMA (three devices)
  - d. Any other combinations of the 3 components (ICS, LAMA and LABA)

The date of the first prescription of Trelegly 100 or MITT between May 22, 2019 and May 5, 2022 will be identified as the index date.

Only SITT users of Trelegly 100 Ellipta with COPD indication will be eligible in this study.

MITT user will be defined as overlapping prescriptions of LAMA, ICS, and LABA, in either two or three devices. Inhaled respiratory medicines have different indications e.g. COPD only, asthma only, or both COPD and asthma. Among medicines composing MITT, at least one medicine must have an indication of COPD at the timing of prescription by considering that the indication of a medicine may

change during the study period. The initial inhaler triple therapy initiation during the identification period that will be used to mark the index date will be defined as the date when the 3rd component is added to the treatment regimen (or 2nd/3rd component if a dual therapy [e.g. ICS/LABA or LAMA/LABA] is added to a monotherapy).

After identifying MITT use by the above rules, continuation of the MITT use will be determined by the rules for exposure continuation described in Sec 8.3.1.1.

All patients who have at least one day of overlap of all 3 components will be classified as MITT users as a base case analysis. The definition of MITT exposure including only one day of overlap of ICS, LABA and LAMA on the index date may overestimate the MITT exposure, and thus another option to include patients who have at least 14 days (index date plus 13 days) of overlap of all 3 components will be given as a sensitivity analysis.

Trelegy 100 or MITT prescriptions in the database will be defined using Anatomical Therapeutic Chemical (ATC) codes (atccode) and Health claim code (receiptcode).

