## Variables

### Exposures

There are two types of triple therapy: single inhaler triple therapy (SITT) (Trelegy 100 only) and MITT as described below. Exposures of this study are Trelegy 100 (SITT) and MITT.

1. Single inhaler triple therapy (SITT):
  - a. Trelegy 100 (Fluticasone furoate (FF)/Umeclidinium bromide (UMEC)/ Vilanterol trifrenatate (VI) delivered in an Ellipta inhaler)
  - b. SITTs other than Trelegy 100 (for secondary objective-d) only)
2. Multiple inhaler triple therapy (MITT):
  - a. LAMA combined with fixed dose ICS/LABA (two devices), or
  - b. Fixed dose LAMA/LABA with ICS (two devices), or
  - c. ICS, LABA, and LAMA (three devices)
  - d. Any other combinations of the 3 components (ICS, LAMA and LABA)

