### 8.2.1. Inclusion criteria

To be included in the study population, patients must meet all of the following criteria:

- Aged 40 years or older on the index date  
As 96% of the patients with COPD were aged 40 years or older in the Ministry of Health, Labour and Welfare (MHLW)'s Patient Survey (2017), the target of this study was set at patients aged 40 years or older.
- Patients with records of ICD-10 codes for COPD (J42, J43 or J44), one record at the index date and additional 2 records (outpatient visit or hospital admission) in the 360 days look-back period [index date, index date -360 days]. This criterion is to exclude patients with infrequent visits who may not be COPD patients, and to secure, collection of patient characteristics data in the look-back period.
- At least one record (outpatient visit or hospital admission) with any ICD-10 codes in the 180 days prior to the start date of look-back period [index date – 360 days, index date – 540 days]. This criterion is to secure patient records throughout the look-back period.
- Two study populations will be set up in Trelegy 100 and MITT users, respectively; COPD patients who started Trelegy 100 or MITT between May 22, 2019 and May 5, 2022 (overall users), and subpopulations of the overall users without any triple therapies in the 360-day look-back period (incident users). Pneumonia occurrence in overall users as well as incident users will be calculated to have good generalizability of study results, since incident users will be a part of overall users. The first use of Trelegy 100 or MITT in the identification period will be included as overall cases. The index date for MITT overall users will be the first prescription date after the launch date of Trelegy 100 (May 22, 2019). In the identification of incident users, “any triple therapies in the look-back period” refer to triple therapies with only COPD indication, mixture of COPD and asthma indications, and only asthma indication.

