Continuation of exposure to Trelegy 100 or MITT in the look-back period will be defined by using “prescription period”, “gap” and “grace period” in the same manner as that in the follow-up period. This approach is applied forwards (and not backwards) in the look-back period and before the look-back period to identify any triple therapy during the look-back period.

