#### **8.7.3.3. Sensitivity analysis**

The primary endpoints and explanatory analysis will be performed by the following conditions. When one of the 3 conditions are applied, other 2 conditions will not be applied but original conditions will be kept.

- One of inclusion criteria is changed from “patients with ICD-10 codes for COPD (J42, J43 or J44)” to “patients with ICD-10 codes for COPD (J42, J43 or J44) and with prescription of any inhaled medicine with the indication of COPD”, at the index date and on at least 2 visits (outpatient visit or hospital admission) in the look-back period
- Overlap of 3 components for MITT group is changed from at least 1 day to at least 14 days (including the index date)
- Follow-up period is changed from maximum 360 days to maximum 1,440 days (after the index date)

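### One day of overlapping estimated supply counts as MITT, so a change between ICS/LABA and LAMA/LABA can enter the comparator as incident triple therapy

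*Protocol*

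**What the plan says.** Protocol Section 8.3.1 defines the comparator by overlap alone: "MITT user will be defined as overlapping prescriptions of LAMA, ICS, and LABA, in either two or three devices". The list of combinations, in the abstract and again in 8.3.1, ends with a catch-all: "Any other combinations of the 3 components (ICS, LAMA and LABA"). The base-case threshold is one day: "All patients who have at least one day of overlap of all 3 components will be classified as MITT users as a base case analysis". Patients are indexed on the day on which the last missing "component is added to the treatment regimen".

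Incident users are those "without any triple therapies in the 360-day look-back period (incident users") (Section 8.2.1). On finding triple therapy before the index date, Section 8.3.1.1 says: "This approach is applied forwards (and not backwards) in the look-back period and before the look-back period to identify any triple therapy".

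The same section ends MITT exposure 30 days after the overlapping period ends, takes 30 days as the standard prescription, and estimates supply from the package insert. Section 8.9 adds that dosage is not recorded for inhaled drugs.

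Section 8.3.1 concedes that the one-day rule may overstate MITT exposure. Section 8.7.3.3 lists the response: "Overlap of 3 components for MITT group is changed from at least 1 day to at least 14 days (including the index date"). No section mentions a change from one dual inhaler to another.

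**The concern.** The primary question compares Trelegy 100 with patients who take ICS, LAMA and LABA from separate inhalers. A patient whose ICS/LABA is replaced by LAMA/LABA before the old inhaler is used up meets the MITT definition on paper, with the LABA counted twice, but has in fact stopped the ICS. In the reverse change the LAMA has been stopped. Neither is triple therapy.

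This entry route is one-sided, because a single Trelegy 100 prescription always contains all three drugs. Section 8.9 offers reassurance only if limitations act similarly in both groups, so it does not cover this one. Propensity weighting does not repair it either: a patient changed from ICS/LABA and a patient stepped up from ICS/LABA have the same value for immediate previous treatment (Section 8.3.3.1), and weighting balances baseline covariates, not misclassified exposure.

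The rule can also reach Trelegy patients. If someone makes such a change and later starts Trelegy 100, the change can become a MITT index date (when it falls in the identification period) or count as prior triple therapy (when it falls in the look-back). How often this happens is not known.

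**Working it through.** **1. Does the definition admit a switcher?** Suppose ICS/LABA supply runs to day 0 or beyond and LAMA/LABA is prescribed on day 0.
- ICS, LABA and LAMA overlap for at least one day in two devices, so the definition and the catch-all are met.
- LAMA is the third component, so day 0 is the index date.
- With no triple therapy in the preceding 360 days and the other criteria met, the patient is an incident MITT user.
- Nothing in Sections 8.2.1 to 8.3.1.1 requires an ICS-containing prescription on or after day 0, or separates add-on from replacement.

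**2. Time booked as MITT.** Overlap L plus the 30-day grace period. With a 30-day prescription, L = 1 to 30 gives 31 to 60 days.

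**3. What the 14-day analysis leaves.** If leftover supply is uniform on 1 to D days (assumption), the share with at least 14 days is (D - 13)/D:
- D = 30: 17/30 = 57%
- D = 20: 7/20 = 35%
- D = 14: 1/14 = 7%
- D = 7: 0%

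**4. Reproduce Table 1 (Section 8.5.1).** Total events E = rate × (N_T + N_M), split HR × N_T : N_M. SE = √(1/E_T + 1/E_M) and P(observed HR > 3) = Φ(ln(HR/3)/SE). For 1935/1311 users, 8% and true HR 2.5:
- E = 0.08 × 3246 = 259.7
- E_M = 259.7/(1 + 2.5 × 1935/1311) = 55.4, and E_T = 204.3
- SE = 0.1515, z = -0.1823/0.1515 = -1.203, P = 11.4%, as printed.

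All 40 cells reproduce to within 0.05 percentage points. Table 1 makes no allowance for misclassified exposure.

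**5. Effect on the primary HR.** This step concerns switchers whose ICS was stopped. Let f be their share of MITT patients, d = 31 to 60 days their follow-up, T the mean follow-up of true MITT users, and r the pneumonia hazard ratio with ICS versus without. Then

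w = f·d / (f·d + (1 - f)·T), and observed HR = true HR / (1 - w + w/r).

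f, r and T are assumptions; the documents give none of them. The last two columns use the 1935/1311, 8% scenario, with the SE held at its Table 1 value.

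| f | r | d | T | w | factor | P(>3), true HR 2.5 | P(>3), true HR 3 |
|---|---|---|---|---|---|---|---|
| none | - | - | - | 0 | 1 | 11.4% | 50.0% |
| 5% | 1.5 | 31 | 360 | 0.005 | 1.002 | 11.6% | 50.4% |
| 10% | 2 | 60 | 180 | 0.036 | 1.018 | 13.9% | 54.5% |
| 20% | 2 | 60 | 180 | 0.077 | 1.040 | 17.2% | 59.7% |
| 30% | 2 | 60 | 360 | 0.067 | 1.034 | 16.4% | 58.4% |
| 30% | 2 | 60 | 180 | 0.125 | 1.067 | 21.8% | 65.7% |

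Top row by hand: w = 0.3 × 60/(0.3 × 60 + 0.7 × 180) = 18/144 = 0.125; factor = 1/(1 - 0.125 + 0.0625) = 1.067. A true HR of 2.5 becomes 2.50 to 2.67 over the range, and a true HR of 3 becomes 3.00 to 3.20.

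**6. Direction.** If switchers have the higher hazard, for example twice that of true MITT users (assumption), the same w = 0.125 gives 1/(1 - 0.125 + 0.25) = 0.889, and the HR is pushed down.

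**The case against.** The protocol discloses the weakness and plans a sensitivity analysis of the primary endpoint, which fully removes changes made within a week of run-out. That stands. The 57% surviving figure depends on leftover supply being uniform over a whole prescription, which nothing in the documents supports or refutes. The analysis is still only partial, because it tests the length of overlap and not whether an inhaler was replaced.

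It can also be said that an added component implies an add-on, and that prescription periods are left to the SAP. But Section 8.3.1 itself fixes the classification, and it rests on overlap alone.

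Three stronger readings are tempting, and the documents do not support them.
- *The primary HR could be inflated by up to 18%.* The factor 1.176 follows from f = 30% and r = 2 with w set equal to f. That describes only the first weeks, or a plan without censoring. Section 8.3.1.1 ends follow-up 30 days after the overlap, and the primary estimate is a single HR over up to 360 days.
- *Only the MITT group carries time off ICS.* Entry through leftover supply is specific to MITT, but a patient who stops Trelegy 100 is followed through the same 30-day grace period.
- *True Trelegy starters are diverted in numbers that matter.* The route exists, but no figure in the documents allows its frequency to be estimated.

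**Conclusion.** The definition admits patients whose inhaler was replaced as incident MITT users, and the planned 14-day analysis removes only some of them. This is a real, one-sided weakness in the primary comparator, and worth correcting because the correction is cheap.

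Its effect on the primary HR is probably small: a factor of about 1.002 to 1.067 with 5-30% switchers, an ICS hazard ratio of 1.5-2 and mean true-MITT follow-up of 180-360 days. The top value needs the least favourable end of every assumption at once. The sign is not established, since the factor falls below 1 if switchers are at higher pneumonia risk. Near the HR > 3 threshold even a small shift matters somewhat: at a true HR of 2.5 in the smallest scenario, the probability of a false signal moves from 11.4% to between 11.6% and 21.8%.

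**What to change.** In Section 8.3.1, state that an overlap of ICS/LABA with LAMA/LABA, in either order, is not MITT unless both inhalers are prescribed on the same date. Apply the same rule when identifying triple therapy in the look-back (Sections 8.2.1 and 8.3.1.1). The rule uses index-day information only, so it does not condition on later refills. It costs protocol wording, one programming condition and slightly fewer MITT patients, including a few who truly use both dual inhalers but collect them on different days. It does not reach ICS/LABA replaced by LAMA alone, which looks the same as an add-on on the index date.

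An analysis requiring all three components to be prescribed on the index date may be added, but only as a strict sensitivity analysis. Its description should say that it also removes genuine add-ons, such as LAMA added to ICS/LABA between refills, and may cost many MITT patients. It should not be described as separating add-on from replacement.

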### 8.3.1.1. Continuation of exposure

[figure not shown]

Figure3 Exposure period

- 1) Gap (variable): Actual period between 2 consecutive prescriptions
- 2) Grace period (constant): The threshold used to determine if an interruption in therapy causes a patient to be considered non-persistent

Continuation of exposure will be defined by using “prescription period”, “gap” and “grace period” (see Figure3).

Prescription period: Treatment period estimated by dosage in package insert (as described in a separate “statistical analysis plan”)

Gap: Actual period between 2 consecutive prescription periods

Grace period: The threshold used to determine discontinuation of treatment

In this study, we set the “grace period” at 30 days.

If a gap between 2 consecutive prescription periods is 30 days or less, the treatment is considered continuation.

If a gap between 2 consecutive prescription periods is 31 days or more, the treatment is considered discontinuation.

Japan’s medical fee system recommends careful consideration for long-term prescription more than 30 days. Restrictions on prescription period for 14 days right after the launch was not applied to Trelegy 100. Based on these situations, we regarded 30 days as a standard prescription period for both Trelegy 100 and MITT. By considering 30-day prescription, potential delay in physician visits and missing medicine, the grace period was set to 30 days.

Exposure period in follow-up period will be defined as the period starting at the index date and ending at 30 days (grace period) after the end date of the final prescription period\* of Trelegy 100 or MITT during 360 days after the index date. If the final prescription period starts before the end date of the previous prescription period, the overlapped days of the 2 prescription periods will be added to the grace period (30 days) in calculating the end date of the final prescription period.

\*Final prescription period of Trelegy 100 or MITT will be defined as follows:

- 1) Subsequent prescription period of Trelegy 100 or MITT started 31 days or more (longer than grace period) after the end date of the last prescription period. In MITT group, the end date of the last prescription period is the end date of overlapping prescription period.
- 2) MITT includes a variety of combination of ICS/LAMA/LABA, and only the change in components of MITT is not considered discontinuation.

Continuation of exposure to Trelegy 100 or MITT in the look-back period will be defined by using “prescription period”, “gap” and “grace period” in the same manner as that in the follow-up period. This approach is applied forwards (and not backwards) in the look-back period and before the look-back period to identify any triple therapy during the look-back period.

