**Figure1 Study design**

Identification of the study population will be conducted using health insurance claims data (outpatient and inpatient) and Diagnosis Procedure Combination (DPC) data. Patients surveyed are aged 40 years or older at the start date of prescription (index date) for Trelegy 100 or MITT during the 1,080-day identification period (from May 22, 2019 to May 5, 2022).

In this protocol, one month is defined as 30 days based on the manner of Post-marketing Surveillance in Japan.

In this study, data will be collected retrospectively with the 1,080-day identification period to have as much patient data as possible within the time frame to submit study results for the reexamination application for Trelegy 100. We plan to conduct data review in 2022 as described at the bottom of ABSTRACT, and we need time to agree on the protocol with PMDA after the endorsement by Protocol Review Committee (PRC), and thus we prepared this protocol in 2020.

Patients with records of International Statistical Classification of Diseases and Related Health Problems, Tenth Revision (ICD -10) codes for COPD (J42, J43 or J44), one record at the index date and additional 2 records (outpatient visit or hospital admission) in the 360 days look-back period [index date, index date -360 days]. This criterion is to exclude patients with infrequent visits and to secure collection of patient characteristics data in the look-back period.

At least one record (outpatient visit or hospital admission) with any ICD-10 codes in the 180 days

prior to the start date of look-back period [index date – 360 days, index date – 540 days]. This criterion is to secure patient records throughout the look-back period.

Follow-up period will be from the index date (including the index date) to the earliest date of the followings: 1) admission date of hospitalization due to CAP or 2) date of death or 3) end date of exposure period with Trelegy 100 or MITT by discontinuation (defined in 8.3.1.1. continuation of exposure), or 4) 360 days after the index date.

In base case analysis, the 360-day follow-up period will be applied, while the 1,440-day follow-up period will be used in sensitivity analysis.

The reason for the 360-day follow-up period is based on the article by Suissa et al. which demonstrated that the effect of ICS on pneumonia occurrence among COPD patients peaked in the first year of use.

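### Section 8.3.1.1 writes the base-case 360-day window into the exposure definition that ends follow-up, so the 1,440-day sensitivity analysis, applied literally, would close soon after day 360

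*Protocol*

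**What the plan says.** Section 8.1 ends follow-up at the earliest of CAP admission, death, and two further stops. Stop 3 is the "end date of exposure period with Trelegy 100 or MITT by discontinuation (defined in 8.3.1.1. continuation of exposure"). Stop 4 is a fixed maximum: "4) 360 days after the index date". Stop 3 takes its meaning from section 8.3.1.1.

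Section 8.3.1.1 describes the exposure period within follow-up as "ending at 30 days (grace period) after the end date of the final prescription period", a footnoted term, and limits that final period to prescriptions "of Trelegy 100 or MITT during 360 days after the index date". The same section sets the discontinuation rule, "If a gap between 2 consecutive prescription periods is 31 days or more, the treatment is considered discontinuation", and gives the usual supply length: "we regarded 30 days as a standard prescription period for both Trelegy 100 and MITT".

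Section 8.7.3.3 lists three sensitivity conditions, applied one at a time. The third is: "Follow-up period is changed from maximum 360 days to maximum 1,440 days (after the index date"). Section 8.1 likewise assigns 360 days to the base case and 1,440 days to the sensitivity analysis. Neither place mentions the window in 8.3.1.1.

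The Definition of terms (section 1) defines the exposure period as running from the index date to 30 days after the end of the final prescription. It contains no 360-day limit.

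**The concern.** A constant that belongs to the base case sits inside a general definition, and that definition ends follow-up. In the base case this does no harm, because stop 4 closes follow-up at day 360 anyway. In the 1,440-day analysis stop 4 moves, and stop 3 becomes the binding rule for anyone still on treatment after a year. If the 360-day window stays, refills after day 360 do not count and the extra follow-up is cut to a few weeks.

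This is the only planned comparison of Trelegy 100 with MITT that looks past the first year. Section 8.1 justifies the 360-day base case by a published finding that the ICS effect on pneumonia peaks in the first year of use, and the 1,440-day analysis is the check on that choice. If it shared nearly all its person-time with the base case, the two HRs would agree largely because they rest on the same data. That agreement could then be reported as robustness to longer follow-up. Independent double programming (8.6.2, 8.8) would not reveal this if both programmers followed the same sentence.

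**Working it through.** **1. The plan's calendar figures reproduce.**
- May 22, 2019 to May 5, 2022 is 1,080 days inclusive.
- May 5, 2022 plus 360 days is Apr 30, 2023, the stated end of the study period.
- May 22, 2019 to Apr 30, 2023 is 1,440 days inclusive, which matches the sensitivity maximum.

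**2. Latest exposure end under the literal wording.**
Inputs from 8.3.1.1: window 360 days, standard supply 30 days, grace 30 days.

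Latest end ≈ window + supply + grace = 360 + 30 + 30 = day 420.

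This is not a hard bound. A 60-day supply gives 360 + 60 + 30 = day 450, and 8.3.1.1 adds overlapped days to the grace period. With day 420, about 60 of the 1,080 extra days (361 to 1,440) could be used.

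**3. Share of the extra on-treatment time that is used.**
Assumptions, none of them from the documents:
- index dates uniform over the 1,080 days;
- constant discontinuation hazard λ after day 360;
- CAP and death ignored;
- 1,440 days read as a maximum, as in 8.7.3.3, with data ending Apr 30, 2023.

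Observable days beyond day 360 are x = 0, 1, …, 1,079 across index dates, with mean 539.5. For a patient still exposed at day 360, the mean extra on-treatment time with a cap of c days is the average over x of (1 − exp(−λ·min(c, x)))/λ. When λ = 0 it is the average of min(c, x).

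| Discontinuation hazard | Uncapped (days) | Stop at day 420 (days) | Used | Lost |
|---|---|---|---|---|
| None | 539.5 | 58.3 | 10.8% | 89.2% |
| ln2/360 per day (half stop per 360 days) | 300.6 | 55.1 | 18.3% | 81.7% |
| Twice that | 198.1 | 52.1 | 26.3% | 73.7% |

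Check of the first row: (0 + 1 + … + 59 + 1,020 × 60)/1,080 = (1,770 + 61,200)/1,080 = 58.3, and 58.3/539.5 = 10.8%. With a stop at day 450 the shares used are 16.0%, 26.4% and 36.9%, so 63% to 84% is lost.

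**4. Effect on total person-time.**
Let p be the proportion still exposed at day 360, λ = −ln(p)/360, and a the data days available after each index date. Mean follow-up with a stop at day T is the average over index dates of (1 − exp(−λ·min(T, a)))/λ. For p = 0.5, λ = 0.001925 and the base case is 0.5/0.001925 = 260 days.

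| Assumed p | Base case, day 360 | Literal, day 420 | Window moved to 1,440 |
|---|---|---|---|
| 20% | 179 days | 189 (1.06×) | 214 (1.20×) |
| 50% | 260 days | 287 (1.11×) | 410 (1.58×) |
| 80% | 323 days | 368 (1.14×) | 672 (2.08×) |

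The literal wording adds 6% to 14% to base-case person-time. Moving the window with the analysis adds 20% to 108%.

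**The case against.** The case for leaving the text alone is that the protocol already supplies a sensible reading.

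- Stop 3 is worded as "end date of exposure period with Trelegy 100 or MITT by discontinuation (defined in 8.3.1.1. continuation of exposure"), and a patient still refilling at day 360 has not discontinued.
- The 31-day gap rule carries no time limit.
- The footnote to 8.3.1.1 ties the final prescription period to a later one starting 31 days or more after it ended.
- The Definition of terms has no 360-day limit.
- Stop 4 also reads "4) 360 days after the index date", and everyone accepts that this moves to 1,440, so the same constant in 8.3.1.1 could be expected to move with it.
- Figure 3 and the SAP, which may set the window for each analysis, are not available here.

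Most of this stands. It shows what was probably intended, and it rules out two stronger claims that a reader might infer. One is that every reading gives a wrong end of follow-up. The uncapped reading gives a proper one, because the gap rule plus grace also covers a discontinuation after day 360. The other is that 8.7.3.3 expressly freezes the exposure window by keeping the original conditions. In context that sentence mainly says that the other two sensitivity changes are not made at the same time.

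What the objection does not do is remove the limit from the sentence that defines exposure within follow-up. Section 8.7.3.3 changes the follow-up maximum, and no visible text changes the exposure window. Section 8.3.1.1 leaves the calculation of the prescription period to the SAP but fixes the window itself.

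**Conclusion.** The protocol contradicts itself on when exposure ends: section 8.3.1.1 limits it to a 360-day window, the Definition of terms does not, and the 1,440-day analysis needs the unlimited version. Followed literally, 8.3.1.1 closes that analysis at about day 420 with a 30-day supply and loses roughly 74% to 89% of the intended extra on-treatment time. The loss rests on uniform accrual and on assumed discontinuation from none to twice ln2/360 per day. It falls to 63% to 84% if the stop is day 450.

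A reader might conclude that the sensitivity analysis is bound to repeat the base case. The documents do not support that: it happens only if the literal wording is programmed, and the uncapped reading is the more plausible intent. The point is that the result should not depend on which reading the programmer picks. The primary HR, the base-case incidence rates and Table 1 are unaffected.

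**What to change.** In section 8.3.1.1, replace the fixed limit "of Trelegy 100 or MITT during 360 days after the index date" with one that follows the analysis: prescriptions count up to the maximum follow-up of the analysis concerned, which is 360 days in the base case and 1,440 days in the sensitivity analysis. Align the Definition of terms, stops 3 and 4 in 8.1, and the third condition in 8.7.3.3 with that wording. The existing 31-day gap rule and 30-day grace period then govern the end of exposure over the whole window in both analyses.

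The cost is one phrase in the protocol with its cross-references, and one parameter in the exposure program. No new data are needed and the primary analysis does not change.
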